Evaluating the effectiveness of lung expansion therapy relies upon global parameter measures such as pulse oximetry oxygen saturation and/or arterial blood gas measurements, chest wall auscultation, and assessment of sputum expectoration following therapy sessions. These global parameters do not provide the sensitivity necessary to evaluate regional lung function responses to therapy, as can be viewed with a chest x-ray or CT image. These diagnostic images provide a static view for regional lung volume assessment. They also rely upon the use of radiation. In our study, we will use Electrical Impedance Tomography (EIT) monitoring to measure regional distribution of ventilation during I.S. and EzPAP® lung expansion therapy to better understand how air travels through ventral, mid-ventral, mid-dorsal, and dorsal lung regions and to determine if redistribution of lung volume is time dependent. This non-invasive, non-radioactive/non-radiation producing, technology will provide real time quantifiable data that may be used to explore whether there is a difference in preferential regional distribution of ventilation when comparing resting eupneic ventilation to I.S. and EzPAP lung expansion therapy. We will also evaluate whether there is a difference in regional distribution of ventilation measured immediately after the third lung expansion therapy breathing sequence and post-lung expansion therapy session baseline measurement.

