**SECONDARY RESEARCH QUESTIONS:**

**1. Is there a difference in regional redistribution of ventilation measured immediately after lung expansion therapy when compared to regional distribution of ventilation measured 5-minutes after lung expansion therapy?**

**Null hypothesis:** There is no difference in regional redistribution of ventilation measured immediately after lung expansion therapy when compared to regional distribution of ventilation measured 5-minutes after lung expansion therapy?

**Alternative hypothesis:** There is no difference in regional redistribution of ventilation measured immediately after lung expansion therapy when compared to regional distribution of ventilation measured 5-minutes after lung expansion therapy?

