### 1. Provide target # of subjects (at all sites) needed to complete protocol.

**INSTRUCTIONS:** If this is NOT a database protocol, this number should be the same as the number of subjects needed to obtain statistically significant results.

**Answer/Response:** 30. This is a proof of concept study. No power analysis was performed.

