### 2. Describe expected rate of screen failure/ dropouts/withdrawals from all sites.

**Answer/Response:** No drop out is expected.

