**► IF YES, describe the stratification/ randomization scheme.**

**INSTRUCTIONS:**

The stratification factors and/or the randomization plan should be identified. If there is no randomization component or important patient characteristics that will be used in treatment allocation or data analysis, a statement to this effect should be included.

Stratification factors: These are pretreatment patient characteristics which could be balanced across treatment arms by design or may be used to determine starting dose or treatment allocation.

If randomization is going to be used, the details of the randomization plan should be described.

The description should include:

- the method and timing of randomization
- the type of randomization scheme that will be used in the study
- whether or not the randomization masked/blinded/if so, then to whom is it masked/blinded
- who has access to the randomization scheme

**Answer/Response:** Parallel randomized controlled trial

A recruitment email will be sent to University of Virginia Medical Center employees who represent the target study population. A university of Virginia email distribution list will be used to mass email respiratory therapy and nursing staff working in adult ICU and surgical acute care patient wards. Word of mouth will also be used to heighten awareness about this study. Adult intensive care fellows will also be invited to participate.

The target population will be encouraged to notify a study investigator if they are interested in being screened for eligibility to participate in this study. The study PI and sub-investigators will be responsible for recruitment and enrollment.

A computer generated random numbers generator will be used to randomly assign study subjects into an I.S. or EzPAP® lung expansion therapy group after documentation of informed consent has been recorded. Randomization masking/blinding will not occur in this study. The lung expansion therapy medical device designs and their respective operational differences are impossible to conceal (See images below).

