**Answer/Response:**

**PRIMARY NULL HYPOTHESIS:**

There is no difference in regional distribution of ventilation when comparing Incentive Spirometry (I.S.) lung expansion therapy to EzPAP® lung expansion therapy in healthy adult human subjects

**Alternative hypothesis:** There is a difference in regional distribution of ventilation when comparing Incentive Spirometry (I.S.) lung expansion therapy to EzPAP® lung expansion therapy in healthy adult human subjects?

- Independent variable
  - Lung expansion therapy
    1. Incentive Spirometry

2. EzPAP®

- Dependent variables
  - Regional distribution of ventilation areas of interest
    1. Ventral end-expiratory lung volume impedance
    2. Mid-ventral end-expiratory lung volume impedance
    3. Mid-dorsal end-expiratory lung volume impedance
    4. Dorsal end-expiratory lung volume impedance
- Statistical analysis
  - Frequency (n) and percentage (%) will be used to report descriptive categorical level data.
  - Shapiro-Wilk test of normality will be applied to evaluate distribution of continuous level data. Normally distributed data will be presented as mean and standard deviation and 95% confidence interval. Effect size will be reported as Cohen's *d*.
  - Non-normally distributed data will be reported as median and interquartile range. Effect size will be reported as *r*.
  - Independent samples t-test will be applied to normally distributed continuous data to compare group means, and Mann Whitney-U test will be applied to non-normally distributed data.
  - Statistical significance set a  $P$  (2-tailed)  $\leq .0125$  to reduce risk of Type I error.

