**Answer/Response:**

While participants will not benefit directly from this study, we anticipate that important information will be gained from our EIT monitoring of regional distribution of ventilation. Future patients may benefit from our study findings as we hope to advance clinical understandings associated with these

IRB-HSR # 19661: A descriptive observational pilot study comparing regional distribution of ventilation during lung expansion therapy in healthy human subjects

therapies with use of EIT monitoring. Our findings also have potential to reduce the use of clinically ineffective lung expansion therapy, which has potential for more appropriate utilization of health care resources, benefitting society in general.

The potential benefit for study participants will not be realized directly since our aim is to monitor regional distribution of ventilation in response to I.S. or EzPAP® lung expansion therapy. These therapies are considered to be standards of care in post-operative surgical patients. Loss of dorsal regional lung volume (i.e., atelectasis) is an example of a post-operative pulmonary complication. EzPAP® is a lung expansion therapy that is used as an alternative to I.S. lung expansion therapy for increasing dorsal regional lung volume (i.e., functional residual capacity) in an effort to prevent or reverse atelectasis. When expiratory positive airway pressures of 5, 10, and 15 cmH2O was administered to a small group of healthy human subjects, Garrard et al. (Chest, 1978) found a positive pressure of 15 cmH2O was associated with the greatest FRC increase when compared to zero pressure and baseline FRC measurements. We are unable to identify previous research describing whether regional redistribution of ventilation is sustained after completing I.S. or EzPAP lung expansion therapy.

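### The secondary time question has no analysis that tests it: the plan refers back to a between-device comparison with no time factor, and it does not say whether change over time is assessed by device or overall

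*Combined protocol and SAP*

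**What the plan says.** Under Hypothesis to be Tested, the one secondary question compares regional distribution "measured immediately after lung expansion therapy when compared to regional distribution of ventilation measured 5-minutes after lung expansion therapy". It speaks of lung expansion therapy in general. The alternative hypothesis printed beneath it repeats the null: both state no difference. The Background describes the same contrast as one between distribution "measured immediately after the third lung expansion therapy breathing sequence and post-lung expansion therapy session baseline measurement", again with no device named.

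The secondary analysis plan (Statistical Considerations, question 5) is a three-word reference back to question 4. There the independent variable is device (I.S. or EzPAP) and the outcomes are end-expiratory lung impedance in four regions. The test is given as "Independent samples t-test will be applied to normally distributed continuous data to compare group means", with Mann-Whitney U for non-normal data. The two-tailed threshold is 0.0125, set "to reduce risk of Type I error". Question 2 lists baseline and post-therapy impedance as outcomes but does not separate an immediate from a 5-minute reading.

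Risk/Benefit Analysis, question 1, says the authors found no earlier research on "whether regional redistribution of ventilation is sustained after completing I.S. or EzPAP lung expansion therapy". The randomisation answer says a random number generator will be used to "randomly assign study subjects into an I.S. or EzPAP® lung expansion therapy group"; no ratio is given. On sample size the protocol states "30. This is a proof of concept study. No power analysis was performed", and on attrition "No drop out is expected".

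**The concern.** The question is about time within a person; the analysis it is sent to is about device between persons. If both devices lose the same amount of their effect over five minutes, I.S. and EzPAP differ by as much at 5 minutes as they did immediately after therapy, so a comparison of devices at either time says nothing about the loss. Conversely, a constant device difference could be significant with no change over time at all.

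The obvious repair, a paired test of the two times on all 30 participants, would follow the wording of the question but leave a second gap. The randomised procedures differ in kind: deep breaths on the spirometer, normal breathing through EzPAP. The protocol gives no reason to expect one shared time course, and its own statement of the evidence gap names both devices. An overall test alone could report a weak or absent time effect when one device's effect fades and the other's does not. The trial randomises between devices but would not use that for its time question.

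**Working it through.** **Inputs from the documents.** N = 30, no dropout expected, two parallel arms, four regions, two-sided 0.0125.

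**Inputs assumed.** The documents give no allocation ratio, effect size or SD. I take 15 per arm and let change = 5-minute value minus immediate value, with SD 1 in each arm. Effects are in units of that SD.

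**Step 1: the plan's own figure.** 0.05 / 4 regions = 0.0125, which reproduces the stated threshold. The 0.05 family level is inferred. There is no power or sample-size calculation to reproduce.

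**Step 2: question against analysis.**

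| | Secondary question | Analysis it is sent to |
|---|---|---|
| Contrast | Immediate vs 5 minutes | I.S. vs EzPAP |
| Comparison | Same person, two times | Different persons |
| Outcome | Change over time | Impedance level per region |
| Time factor | Required | None |

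The Brief Summary names a one-way multivariate analysis of variance for the primary hypothesis instead. That has one factor too, so it does not fill the gap.

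**Step 3: pooling, if it were done.** Pooled mean change = (n_I × d_I + n_E × d_E) / (n_I + n_E). With 15 and 15 and d_I = 0, this is d_E / 2: 0.8 becomes 0.4 and 1.0 becomes 0.5. At another ratio the factor is that device's share of the 30. The halving does not depend on the assumed SD.

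**Step 4: power per region at 0.0125.** Simulation with 40,000 or 100,000 replicates per scenario: one-sample t on all 30 changes; one-sample t on one arm of 15; two-sample t on changes between arms (28 df).

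| Change in the two devices | Pooled | One device alone | Device difference |
|---|---|---|---|
| 0 and 0.5 | 10% | 22% (the one that changes) | 12% |
| 0 and 0.8 | 27% | 60% (the one that changes) | 33% |
| 0 and 1.0 | 42% | 83% (the one that changes) | 53% |
| 0.5 and 0.5 | 53.5% | about 22% (each) | not run |
| 0.8 and 0.8 | 95% | 60% (each) | 1.2% |
| 1.0 and 0.5 | 90.5% | not tabulated | 11.5% |
| +0.8 and -0.8 | 0.2% | 60% (each) | 95% |

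The last row is a limiting case only. The 1.2% in the fifth row is the type I error level: a between-device test cannot see a change common to both.

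**Step 5: cost of keeping device in the model.** With a change of 1 SD in both devices, the average-change test has 99.6% power pooled and 99.5% to 99.6% with device in the model. With 0.8 SD in both it is 95% either way.

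**Step 6: precision (95% half-widths).**
- One device: 2.145 / √15 = 0.55 SD
- All 30 pooled: 2.045 / √30 = 0.37 SD
- Device difference: 2.048 × √(2/15) = 0.75 SD

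**The case against.** A reader might infer that the plan averages the two devices. The documents do not support that. No section pools the arms, and the only analysis text keeps them apart by comparing them. The dilution figures therefore describe what would follow from analysing the question as worded, not something the plan commits to.

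A reader might also infer that the devices are likely to move in opposite directions and cancel. Nothing in the documents suggests it; Risk/Benefit Analysis presents EzPAP as an alternative to I.S. with the same aim of raising dorsal lung volume. When both devices move the same way, pooling does well (90.5% for 1.0 and 0.5 SD) and the device difference is poorly powered (11.5%). An average over devices is a legitimate question, and the Brief Summary asks in general terms whether redistribution depends on time. In a 30-person proof-of-concept study, leaving out a formal interaction test can be defended. All of this stands, and it is why the device difference should be estimated rather than tested.

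The strongest objection is that the primary test could be applied to the immediate-to-5-minute change, since the monitoring section speaks of recording impedance changes before and after therapy. It would then be the device-by-time contrast. However, question 4 lists impedance in each region as the outcome, not a change between the two post-therapy times. Even on that reading the contrast would not answer the secondary question: a 0.8 SD change shared by both devices is flagged only 1.2% of the time.

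The remark on sustained redistribution is a comment on the literature, not an objective. It supports reporting by device but does not oblige the study to test an interaction.

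**Conclusion.** The concern holds in this form. The secondary question has no analysis that tests it, and nothing written gives both an overall answer on time and a time course for each device. That is more than missing detail, because the method pointed to answers a different question. This part rests on the text alone.

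The size of any dilution is conditional. It arises only if the two arms are analysed together with no device term, and the halving needs 1:1 allocation. The power figures also need 15 per arm, SD 1 and the effect sizes shown. Under those assumptions, for a change in one device only, power is 27% pooled against 60% in that device at 0.8 SD, and 42% against 83% at 1 SD. Where both devices share a time course, pooling loses nothing.

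The primary comparison is untouched. This is a secondary question in a proof-of-concept study, but the plan should be corrected before analysis.

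**What to change.** Replace the answer to Statistical Considerations, question 5, with text to this effect:

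- For each participant and region, change is the 5-minute value minus the immediate value. State which part of the post-therapy recording supplies each value.
- Fit change on device.
- Test the average change over the two devices at 0.0125 per region, as the answer to the secondary question.
- Report the change for I.S., the change for EzPAP and their difference with confidence intervals, labelled as estimation and not as further tests.

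Correct the alternative hypothesis of the secondary question so that it states a difference.

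No new data are needed: both arms already have five minutes of EIT monitoring after the last breath cycle. The average test keeps the power of a pooled test when the time courses agree. It is still diluted when only one device changes; the by-device estimates are there to show that.

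The cost is three further estimates per region, 3 × 4 = 12 in all. They will be imprecise at 15 per arm: 95% half-widths of about 0.55 SD for each device, against 0.37 SD pooled. Power for the device difference would be limited, about 53% for a 1 SD difference and about 12% for 0.5 SD, so an interval that includes zero should not be read as evidence that the devices share a time course.

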**Study Design: Biomedical**

**1. Will controls be used?**

**Answer/Response:** Yes.

► **IF YES, explain the kind of controls to be used.**

**Answer/Response:** Healthy adult human subjects allocated to receive Incentive Spirometry.

## 2. What is the study design?

Example: case series, case control study, cohort study, randomized control study, single-blind, double-blind, met-analysis, systematic reviews, other. You may also view the IRB-HSR Learning Shot on this topic to help you answer this question.

[http://www.virginia.edu/vpr/irb/learningshots/Writing\\_protocol\\_June09/player.html](http://www.virginia.edu/vpr/irb/learningshots/Writing_protocol_June09/player.html)

**Answer/Response:** Randomized controlled proof of concept descriptive observational study.

## 3. Does the study involve a placebo?

**Answer/Response:** No

► **IF YES, provide a justification for the use of a placebo**

**Answer/Response:**

## Human Participants

**Ages:** 18 – 79 years

**Sex:** Male and Female

**Race:** All

## Subjects- see below

**INSTRUCTIONS:** For question 1-4 below insert an exact #. Ranges or OPEN is not allowed. This # should be the maximum # you expect to need to enroll (i.e. sign consent) If you are only collecting specimens the number of participants should equate to the # of specimens you need. If you are collecting only data from a chart review the number should designate the number of subjects whose medical records you plan to review. Age/ Sex/Race criteria should designate the demographics of participants from whom you will obtain the specimen/data.

### 1. Provide target # of subjects (at all sites) needed to complete protocol.

**INSTRUCTIONS:** If this is NOT a database protocol, this number should be the same as the number of subjects needed to obtain statistically significant results.

**Answer/Response:** 30. This is a proof of concept study. No power analysis was performed.

### 2. Describe expected rate of screen failure/ dropouts/withdrawals from all sites.

**Answer/Response:** No drop out is expected.

### 3. How many subjects will be enrolled at all sites?

**INSTRUCTIONS:** This number must be the same or higher than the # from question # 1 in order to account for the # of screen failures, dropouts, withdrawals described in question # 2.

**Answer/Response:** 30

**4. How many subjects will sign a consent form under this UVa protocol?**

**INSTRUCTIONS:** If the protocol does not have a consent form- the number listed here should reflect such things as the number of subjects from whom specimens will be obtained, the number of charts to be reviewed etc.

**Answer/Response:** 30

**5. Provide an estimated time line for the study.**

**INSTRUCTIONS:** This should include timelines for enrollment (e.g 50 % enrolled in one year, 100% enrolled in two years), completion of follow-up (if applicable) and completion of data analysis.

**Answer/Response:** 100% enrollment within three months.

### Inclusion/Exclusion Criteria

**INSTRUCTIONS:**

- The inclusion and exclusion criteria should be written in bullet format.
- *This item applicable if the study will require consent (verbal or written).* Unless there is a scientific reason for not recruiting a certain type of vulnerable population(e.g. not enrolling fetuses, neonates or children in a study regarding Alzheimer’s) list the following vulnerable populations under either Inclusion or Exclusion criteria below: pregnant women, fetuses, neonates, children, prisoners, cognitively impaired, educational or economically disadvantage, non- English speaking subjects .
- If you will not enroll subjects who do not speak English because certain procedures cannot be carried out if the subject does not speak English (e.g. a survey is not validated in other languages) insert the following as an Inclusion Criteria: Willingness and ability to comply with scheduled visits and study procedures.
- If this is a collection of only retrospective\* specimens or data, the inclusion criteria must include a start and stop date for when specimens/ data will be collected.
- The stop date must be prior to the version date of this protocol.
- \*Retrospective: all specimens are in a lab at the time this protocol is approved by the IRB. All data exists in medical records or records from previous studies at the time this protocol is approved by the IRB.

**1. List the criteria for inclusion**

**Answer/Response:**

- Human subjects 18 – 79 years of age
- Healthy- not receiving in-patient medical care
- Documentation of written informed consent

**2. List the criteria for exclusion**

**Answer/Response:**

- Less than 18 or greater than 79 years of age
- Body mass index > 50
- Excessive chest hair

IRB-HSR # 19661: A descriptive observational pilot study comparing regional distribution of ventilation during lung expansion therapy in healthy human subjects

- Inability to obtain written informed consent
- Inability to follow verbal instructions
- Pregnancy-self reported
- Uncontrolled body movements
- Inability to place EIT electrodes and belt in direct contact with skin where they are projected to come into contact
- Active implants (i.e., cardiac pacemaker, implantable cardioverter-defibrillator [ICD]), or when device compatibility is in doubt.)

**3. List any restrictions on use of other drugs or treatments.**

**Answer/Response:** None

### Statistical Considerations

**1. Is stratification/randomization involved?**

**Answer/Response:** Yes.

**► IF YES, describe the stratification/ randomization scheme.**

**INSTRUCTIONS:**

The stratification factors and/or the randomization plan should be identified. If there is no randomization component or important patient characteristics that will be used in treatment allocation or data analysis, a statement to this effect should be included.

Stratification factors: These are pretreatment patient characteristics which could be balanced across treatment arms by design or may be used to determine starting dose or treatment allocation.

If randomization is going to be used, the details of the randomization plan should be described.

The description should include:

- the method and timing of randomization
- the type of randomization scheme that will be used in the study
- whether or not the randomization masked/blinded/if so, then to whom is it masked/blinded
- who has access to the randomization scheme

**Answer/Response:** Parallel randomized controlled trial

A recruitment email will be sent to University of Virginia Medical Center employees who represent the target study population. A university of Virginia email distribution list will be used to mass email respiratory therapy and nursing staff working in adult ICU and surgical acute care patient wards. Word of mouth will also be used to heighten awareness about this study. Adult intensive care fellows will also be invited to participate.

The target population will be encouraged to notify a study investigator if they are interested in being screened for eligibility to participate in this study. The study PI and sub-investigators will be responsible for recruitment and enrollment.

A computer generated random numbers generator will be used to randomly assign study subjects into an I.S. or EzPAP® lung expansion therapy group after documentation of informed consent has been recorded. Randomization masking/blinding will not occur in this study. The lung expansion therapy medical device designs and their respective operational differences are impossible to conceal (See images below).

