### Lung Expansion Therapy Devices

Incentive Spirometer

EzPAP® System

► **IF YES, who will generate the randomization scheme?**

- Sponsor
- UVa Statistician.  Answer/Response:
- UVa Investigational Drug Service (IDS)
- Other:  Answer/Response: Study investigators.

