- EIT device calibration and signal check
  - Researcher will initiate a PulmoVista 500 EIT monitoring device calibration each day prior to performing new study participant EELI measurements.
  - A skin-electrode signal check will be performed to ensure that a minimum of 15 of 16 electrodes have sufficient contact with the participant's skin surface and signal quality is stable. Researchers will use the following status display and explanation to determine adequacy of electrode contact and signal quality.

Status	Explanation
Gray	Skin-electrode contact is sufficient for measurement to proceed
White	Skin-electrode contact is unstable, measurement will proceed but signal quality may be impaired
Red	Skin-electrode contact is insufficient for measurement to proceed

• M

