3. **Will any additional information be obtained from a potential subject during "prescreening"?**

**Pre-screening** for IRB purposes is the term used to describe activities PRIOR to obtaining Informed Consent and may not include any research procedures.

The activities may involve pre-screening of potential subjects over the telephone or in person is generally performed to determine their initial eligibility for, and, interest in a study and is a common strategy in the recruitment process.

Questions appropriate for pre-screening address the specific inclusion/exclusion criteria for the study and other issues of suitability, for example, an individual's ability to come to the research site multiple times.

It is not appropriate at this point in the process (i.e. prior to obtaining informed consent/enrollment) to gather information that is not directly related to assessing eligibility and suitability (e.g. obtaining complete medical histories, obtaining blood specimens for lab tests).

An additional telephone script is not required, for this pre-screening process, in addition to any scripts required under Recruitment question # 2.

**Answer/Response:** Yes

IF YES, submit any documents that will be used to collect pre-screening information so that the IRB may confirm what questions will be asked.

NOTE: To comply with HIPAA regulations only the minimum necessary information may be collected at this time. This means that only questions pertaining to the Inclusion and Exclusion Criteria may be asked.

IF YES,

DHHS: study team requests a Waiver of Documentation of Consent for Pre-screening questions.

HIPPA:

HIPAA does not apply if:

--no PHI is collected or

--if PHI is collected from a potential subject by an individual from a department that is not part of the HIPAA covered entity.

HIPAA does apply if the collection occurs by individuals\* who work in a department that is part of the HIPAA covered entity.

In this case the collection will be covered under Health Care Operations/

These individuals are those that meet one of the following criteria:

--a UVa student working in the UVa HIPAA Covered Entity\*

--a faculty or staff member in a PAID appointment in the UVA HIPAA Covered Entity\*

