**7. Will the study procedures be started the same day the subject is recruited for the study?**

**Answer/Response:** Optional based on participant's desire and study investigator availability to conduct procedure and monitoring on the same day recruitment occurs.

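### Allocation is tied only to consent and not placed after belt fitting and the signal check, so the plan permits open-label exclusion of a subject whose arm is already known

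*Combined protocol and SAP*

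**What the plan says.** All references are to the combined protocol and SAP.

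- **Timing of allocation.** Statistical Considerations, question 1, has a random numbers generator assign each subject to an I.S. or EzPAP® "lung expansion therapy group after documentation of informed consent has been recorded". The Brief Summary/Abstract says the same in substance. No later condition is given.
- **Openness.** The same answer states: "Randomization masking/blinding will not occur in this study". Recruitment and enrolment belong to the PI and sub-investigators. On who generates the scheme, the entry is "Answer/Response: Study investigators".
- **Contact exclusion.** Inclusion/Exclusion Criteria, question 2, lists "Inability to place EIT electrodes and belt in direct contact with skin where they are projected to come into contact".
- **Signal check.** Biomedical Research, question 1, under EIT device calibration and signal check: "A skin-electrode signal check will be performed to ensure that a minimum of 15 of 16 electrodes have sufficient contact". A red status means measurement cannot go ahead. A white (unstable) status lets it continue.
- **Before consent.** Appendix: Recruitment, question 5, has volunteers pre-screened against the eligibility criteria. Question 3 says pre-screening "may not include any research procedures". Question 4 confirms that nothing beyond answering questions is asked of them.
- **Numbers.** Under Subjects, the number needed, the number enrolled and the number signing consent are each 30, and the form defines the figure as a maximum. On screen failures, dropouts and withdrawals the answer is "No drop out is expected".

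**The concern.** Whether the belt and electrodes make usable contact is both an eligibility matter and the condition for having any outcome at all. It can be physically tested only after consent. If the arm has already been drawn, an open-label investigator decides on contact, or on whether to keep trying for a signal, while knowing which device the subject will use. An exclusion made then can differ between arms, and randomisation no longer protects the comparison. Made before the draw, the same decision is an ordinary screen failure and cannot favour either arm.

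The second consequence is a randomised subject with no EIT data. Statistical Considerations, questions 4 and 5, give no analysis set, replacement rule or missing-outcome rule for such a subject.

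**Working it through.** **1. Order of steps.** Set side by side, the sections give this sequence:

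- Before consent: questions on eligibility only. Chest circumference, belt choice, belt fitting and electrode contact all belong to the study procedures, so none of them can be tested here.
- Consent is documented.
- After consent, in an unstated order: (a) allocation; (b) belt fitting and the 15-of-16 signal check.
- Therapy and monitoring.

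Order (a) then (b) complies with the plan as fully as (b) then (a). The form for question 1 asks for the timing of randomisation, and the answer leaves this point open.

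**2. Who would know the arm.** If (a) comes first, everyone at set-up can know it. In the I.S. session, one investigator both helps apply the EIT interface and teaches the device. The screen concealment described under Regional Distribution of Ventilation Monitoring applies during therapy, so it does not cover set-up.

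**3. The plan's own numbers.** With loss rate d, consents needed = 30/(1 − d). At d = 0 this is 30/1 = 30, which reproduces the stated figure. The plan balances only at zero loss.

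**4. Allowance for contact failure.** The documents give no rate, so d is an assumption.

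| d | Chance of no failure in 30, (1 − d)^30 | Expected failures, 30d | Consents for 30 measured, 30/(1 − d) rounded up |
|---|---|---|---|
| 1% | 0.740 | 0.3 | 30.3 → 31 |
| 2% | 0.545 | 0.6 | 30.6 → 31 |
| 5% | 0.215 | 1.5 | 31.6 → 32 |
| 10% | 0.042 | 3.0 | 33.3 → 34 |

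These figures show how easily the zero-loss premise fails. They do not measure selection bias.

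**5. Precision.** No allocation ratio is stated, so 15 per arm is assumed. One loss is then 1/15, about 7% of an arm. The standardised difference detectable with 80% power at the plan's two-sided 0.0125 (normal approximation) is (2.498 + 0.842) × √(2/n):

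- n = 15: 1.22 SD
- n = 14: 1.26 SD
- n = 13: 1.31 SD
- n = 12: 1.36 SD

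Losing two subjects per arm raises it by about 0.09 SD.

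**6. Selection.** Its size depends on how often contact decisions would differ by arm and how those subjects' impedance would have differed. The documents inform neither, so no figure is offered.

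**The case against.** The strongest reply is that requiring allocation after consent sets an earliest point and not a trigger. Chairside allocation following a passed signal check fits the text, and no section places allocation before set-up. That is correct. What stands is that the plan permits either order, and only one closes the route to selection.

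Other readings a reader might infer are not supported:

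- *That chest hair and uncontrolled movements can be judged only with the belt on.* Both can be covered at pre-screening, which may be in person. Only actual contact and signal need the belt.
- *That randomised subjects may be sent home before their session.* Appendix: Recruitment, question 7, calls same-day procedures "Optional based on participant's desire and study investigator availability to conduct procedure and monitoring on the same day recruitment occurs". The answers that follow explain this mainly as time to decide about consent.
- *That failing the signal check is itself an exclusion.* It is a set-up step, absent from the exclusion list, and no section says a red status excludes the subject.
- *That contact failure will be common.* The set-up text offers five overlapping belt sizes, wetted electrodes and an alternative belt site. It may be rare.

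It is also fair to say that the three matching figures of 30 are an accrual-allowance issue under either order. The target rests on no power calculation, so a loss defeats no stated power.

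**Conclusion.** The point holds as a gap in the specified order. The plan permits an open-label exclusion, or a finding that a subject cannot be measured, after the arm is known, and has no rule for the randomised subject who results. It does not establish that exclusions will be made this way, and a reader should not infer that consent triggers allocation.

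The cost in precision is modest: 1.22 SD to 1.31 SD if each arm falls from 15 to 13, assuming equal arms and a normal approximation. The reason to act is possible selection between arms, unquantified here, which a reordering removes at almost no cost. The conclusion rests on three documented facts: allocation is unmasked, the investigators both generate the scheme and enrol, and contact cannot be tested before consent. It does not depend on any assumed failure rate. This is a change that should be made, not a flaw that invalidates the design.

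**What to change.** - **Statistical Considerations, question 1.** State that allocation is drawn and revealed only after consent, confirmation of all listed exclusions, belt fitting and a passed signal check (at least 15 of 16 electrodes). Contact failures then become screen failures and not randomised losses.
- **Subjects, questions 1 to 4.** State that 30 is the number randomised and that contact failures before allocation do not count towards it. Set the consent ceiling from a stated assumed rate, for example 32 at 5% or 34 at 10%. These cover expected failures only and do not guarantee 30.
- **Statistical Considerations, question 4.** Add one sentence on how any subject who is still randomised without EIT data is reported and analysed.
- **Chest-hair criterion.** Leave it as it is. Using the signal check as its test would change who is eligible, and nothing in the documents treats the two as equivalent.

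The cost is a few sentences and a slightly higher consent figure for IRB approval, with no new procedure, visit or staff. The one small downside is that subjects wear the belt a few minutes longer while the assigned device is explained.
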